### **10.4 Other Response Parameters**

None

## **11. Data Reporting / Regulatory Considerations**

### **11.1 Data Collection**

The data collection plan for this study is to utilize REDCap to capture all treatment, toxicity, efficacy, and adverse event data for all enrolled subjects.

#### **11.1.1 REDCap**

REDCap (Research Electronic Data Capture) is a free data management software system that is fully supported by the Weill-Cornell Medical Center CTSC. It is a tool for the creation of customized, secure data management systems that include Web-based data-entry forms, reporting tools, and a full array of security features including user and group based privileges, authentication using institution LDAP system, with a full audit trail of data manipulation and export procedures. REDCap is maintained on CTSC-owned servers that are backed up nightly and support encrypted (SSL-based) connections. Nationally, the software is developed, enhanced and supported through a multi-institutional consortium led by the Vanderbilt University CTSA.

### **11.2 Regulatory Considerations**

#### **11.2.1 Institutional Review Board/Ethics Committee Approval**

As required by local regulations, the Investigator will ensure all legal aspects are covered, and approval of the appropriate regulatory bodies obtained, before study initiation.

Before initiation of the study at each study center, the protocol, the ICF, other written material given to the patients, and any other relevant study documentation will be submitted to the appropriate Ethics Committee. Written approval of the study and all relevant study information must be obtained before the study center can be initiated or the IP is released to the Investigator. Any necessary extensions or renewals of IRB approval must be obtained for changes to the study,

such as amendments to the protocol, the ICF, or other study documentation. The written approval of the IRB together with the approved ICF must be filed in the study files.

The Investigator will report promptly to the IRB any new information that may adversely affect the safety of the patients or the conduct of the study. The Investigator will submit written summaries of the study status to the IRB as required. On completion of the study, the IRB will be notified that the study has ended.

All agreed protocol amendments will be clearly recorded on a protocol amendment form and will be signed and dated by the original protocol approving signatories. All protocol amendments will be submitted to the relevant institutional IRB for approval before implementation, as required by local regulations. The only exception will be when the amendment is necessary to eliminate an immediate hazard to the trial participants. In this case, the necessary action will be taken first, with the relevant protocol amendment following shortly thereafter.

Once protocol amendments or consent form modifications are implemented at the lead site, Weill Cornell Medicine, updated documents will be provided to participating sites, as applicable. Weill Cornell Medicine must approve all consent form changes prior to local IRB submission.

Relevant study documentation will be submitted to the regulatory authorities of the participating countries, according to local/national requirements, for review and approval before the beginning of the study. On completion of the study, the regulatory authorities will be notified that the study has ended.

#### **11.2.2 Ethical Conduct of the Study**

The Investigators and all parties involved should conduct this study in adherence to the ethical principles based on the Declaration of Helsinki, GCP, ICH guidelines and the applicable national and local laws and regulatory requirements.

This study will be conducted under a protocol reviewed and approved by the applicable ethics committees and investigations will be undertaken by scientifically and medically qualified persons, where the benefits of the study are in proportion to the risks.

#### **11.2.3 Informed Consent**

The investigator or qualified designee must obtain documented consent according to ICH-GCP and local regulations, as applicable, from each potential subject or each subject's legally authorized representative prior to participating in the research study. Subjects who agree to participate will sign the approved informed consent form and will be provided a copy of the signed document.

The initial ICF, any subsequent revised written ICF and any written information provided to the subject must be approved by IRB prior to use. The ICF will adhere to IRB requirements, applicable laws and regulations.

#### **11.2.4 Compliance with Trial Registration and Results Posting Requirements**

Under the terms of the Food and Drug Administration Modernization Act (FDAMA) and the Food and Drug Administration Amendments Act (FDAAA), the Sponsor-Investigator of the trial is solely responsible for determining whether the trial and its results are subject to the requirements for submission to <http://www.clinicaltrials.gov>. Information posted will allow subjects to identify potentially appropriate trials for their disease conditions and pursue participation by calling a central contact number for further information on appropriate trial locations and trial site contact information.

#### **11.2.5 Record Retention**

Essential documents are those documents that individually and collectively permit evaluation of the study and quality of the data produced. After completion of the study, all documents and data relating to the study will be kept in an orderly manner by the Investigator in a secure study file. Essential documents should be retained for 2 years after the final marketing approval in an ICH region or for at least 2 years since the discontinuation of clinical development of the IP. In addition, all subjects medical records and other source documentation will be kept for the maximum time permitted by the hospital, institution, or medical practice.

### **12. Statistical Considerations**

#### **12.1 Study Design/Endpoints**

This is an open-label, single arm, single center non-randomized Phase II study to investigate the efficacy and safety of KN046 in patients with advanced thymic carcinoma who have progressed on prior immune checkpoint inhibitor therapy. Subjects will be treated with KN046 5 mg/kg q2wk.

A Simon's two-stage design will be used. Under the optimum design criterion, a sample size of 29 is required to test a null hypothesis of  $H_0: \pi \leq 0.05$  versus an alternative hypothesis of  $H_1: \pi \geq 0.2$  with a one-sided significance level of 0.047 and 80.11% power, where  $\pi$  is the true proportion of successes. This design results in an expected sample size of 17.624 and a probability of early termination of 0.599. If the number of responses is less than or equal to 0 out of 10 subjects in the first stage then the trial will be stopped. If the trial proceeds to the second stage, 29 subjects in total will be studied. If 3 or less responses are observed, then KN046 is rejected.

#### **12.2 Sample Size/Accrual Rate**

29 subjects are anticipated to be enrolled in this protocol.

A Simon's two-stage design will be used. Under the optimum design criterion, a sample size of 29 is required to test a null hypothesis of  $H_0: \pi \leq 0.05$  versus an alternative hypothesis of  $H_1: \pi \geq 0.2$  with a one-sided significance level of 0.047 and 80.11% power, where  $\pi$  is the true proportion of successes. This design results in an expected sample size of 17.624 and a probability of early termination of 0.599. If the number of responses is less than or equal to 0 out of 10 subjects in the first stage then the trial will be stopped. If the trial proceeds to the second stage, 29 subjects in total will be studied. If 3 or less responses are observed, then KN046 is rejected. A total sample size of 29 subjects are planned.

### **12.3 Stratification Factors**

None

### **12.4 Analysis of Endpoints**

#### **12.4.1 Analysis of Primary Endpoints**

Primary endpoint: Response rate. Responses will be assessed according to RECIST 1.1.

For ORR analysis, 95% confidence interval (CI) will be calculated using the Clopper Pearson method.

#### **12.4.2 Analysis of Secondary Endpoints**

Secondary endpoints: duration of response, PFS, OS, safety and tolerability.

Safety will be assessed by monitoring all adverse events, including serious adverse events, immune-related adverse events (irAEs), infusion reactions, regular monitoring of bloodwork (including CPK and troponin levels), vital signs, EKGs, and echocardiograms. Kaplan–Meier estimator will be used to estimate PFS and OS.

Safety and tolerability analysis will be performed on SS. The safety endpoints will be tabulated using descriptive statistics.

The extent of exposure to KN046 will be characterized by duration (weeks), number of administrations, cumulative dose (mg/kg), dose intensity (mg/kg/week), relative dose intensity (actual dose given/planned dose), number of dose reductions, and number of dose delays.

Safety assessments will be based on review of the incidence of AEs, adverse drug reactions (ADRs), and changes in vital signs, ECGs, body weight, and laboratory values (hematology and serum chemistry).

For a single proportion, such as PFS rate, and OS rate, 95% CIs will be calculated using the Clopper Pearson method. For time to event variable, for example DOR, PFS and OS analysis, the Kaplan-Meier method will be used to estimate parameters (including the median with corresponding 2-sided 95% CIs). The PFS and OS rates will be estimated with corresponding 95% CIs at appropriate time points, e.g., at 6 and 12 months.

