### **3. Study Design**

#### **3.1 Overall Design**

This is a Phase II, open-label, single-center, single arm study in subjects with advanced thymic carcinoma after failure of platinum-based combination chemotherapy. Subjects should have documented progressive disease after a platinum-based combination chemotherapy and an immune checkpoint inhibitor (PD-1 or PD-L1 antibodies). Subjects will be treated with KN046 at 5 mg/kg Q2W.

For individual subjects, the study begins with a screening period to assess eligibility up to and including 28 days prior to the first dose of KN046.

The treatment period begins on Day 1 of Cycle 1. All subjects will be treated with KN046 at 5 mg/kg Q2W intravenously until progressive disease according to RECIST 1.1, unacceptable toxicity, completion of 2 years of KN046 treatment, start of a new anti-cancer therapy, death, lost follow-up or withdrawal of informed consent, whichever comes first. After completion of 2 years of KN046 treatment, if investigator considers that subject continuing KN046 treatment will obtain clinical benefit, KN046 will be administered on a compassionate basis under the treating physician's responsibility. Treatment of KN046 beyond initial investigator evaluated progression (either clinical or imaging progression per RECIST 1.1 criteria) is allowed if the subject has an investigator assessed clinically stable status and is tolerating the treatment that meets the "Criteria for Continuation of Treatment Beyond Progression". Rechallenge with KN046 will be allowed if a patient responded and stopped the treatment for reasons other than progression while on treatment or toxicity.

Tumor evaluation will be performed at baseline, every 8 weeks in the first 12 months and every 12 weeks thereafter. Tumor evaluation will continue until confirmed progressive disease per RECIST 1.1, starting new anti-cancer therapy, withdrawal of informed consent, or subject's death, whichever comes first. Once objective response is observed, response should be confirmed by a second scan at approximately 8 weeks apart (no earlier than 4 weeks and no later than 8 weeks).

Clinical and laboratory assessments will be performed as described in Section 6.

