After the last dose of KN046, subject will be asked to have an end-of-treatment (EOT) visit, a 30-day safety follow up visit, a 90-day safety follow up visit and overall survival follow up. EOT visit must be performed as soon as possible and within 14 days of last dose of KN046. Subjects who do not have progressive disease after EOT visit will continue tumor assessment until progressive disease, start of a new anti-cancer therapy, subject withdrawal of informed consent or death, whichever comes first. Subjects will be contacted every 12 weeks to obtain information pertaining to survival status until death, lost to follow-up, withdrawal of consent to survival follow-up or the end of study.

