#### **7.10 Duration of Follow Up**

Subjects will be followed for 2 years after removal from study or until death, whichever occurs first. Subjects removed from study for unacceptable adverse events will be followed until resolution or stabilization of the adverse event.

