#### **8.1 Criteria for subject withdrawal**

A subject must be withdrawn from KN046 in the event of any of the following:

- Confirmed PD per RECIST 1.1 and the investigator consider that continuing KN046 treatment will not benefit (note: subject receiving KN046 may continue past the initial determination of PD if the subject meets the criteria of clinically stable);
- Significant clinical deterioration (clinical progression) is defined as new symptoms that are deemed by the investigator to be clinically significant or significant worsening of existing symptoms;
- Therapeutic failure requiring urgent additional anticancer drug;
- Unacceptable toxicity (if a subject does not occur RECIST 1.1 defined confirmed PD, the subject will be asked to continue tumor assessment until RECIST 1.1 defined PD is confirmed);
- Occurrence of pregnancy;
- Use of a nonpermitted concomitant drug as defined in Section 7.4.2 where the predefined consequence is withdrawal from KN046;

- Withdrawal of the subject's consent to continue KN046 (if a subject withdraws consent, the subject will be asked to continue tumor assessments if RECIST 1.1 defined confirmed PD does not occur);
- Noncompliance.
- Withdrawal of the subject's consent. If the subject withdraws consent, it must be clearly stated if the subject is also withdrawing their consent from the post-treatment follow-up assessments;
- Participation in any other therapeutic study during the Treatment Phase of this study; however, subjects will continue to be followed for new anticancer therapy and for survival;
- Lost to follow-up.

In case of withdrawal from the study, the assessment schedule for end-of-treatment visit should be performed if possible and focus on the most relevant assessments. Subjects will be asked to continue safety and long-term follow-up, which includes the collection of data on survival and subsequent anticancer therapy.

The investigator must determine the primary reason for the subject's withdrawal as completely and accurately as possible. The reason for participant discontinuation or withdrawal from the study will be recorded in the medical record and RedCap.

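### Section 12.4.2 assigns Clopper-Pearson intervals to PFS and OS rates but estimates PFS and OS by Kaplan-Meier; the two do not generally match once a patient is censored before 6 or 12 months

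*Combined protocol and SAP*

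**What the plan says.** Three statements in section 12.4.2 bear on the point.

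- On the estimator: "Kaplan–Meier estimator will be used to estimate PFS and OS". A later sentence repeats Kaplan-Meier for DOR, PFS and OS.
- On the interval: "For a single proportion, such as PFS rate, and OS rate, 95% CIs will be calculated using the Clopper Pearson method". PFS rate and OS rate are the only examples given. ORR has its own Clopper-Pearson statements in sections 12.4.1 and 12.6.2.
- On the time points: "The PFS and OS rates will be estimated with corresponding 95% CIs at appropriate time points, e.g., at 6 and 12 months". This sentence follows the Kaplan-Meier sentence and names no interval method.

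Other sections determine whether status at 6 or 12 months will be known.

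- Section 3.1, tumor assessment: "Tumor evaluation will continue until confirmed progressive disease per RECIST 1.1, starting new anti-cancer therapy, withdrawal of informed consent, or subject's death". Scans can therefore end before progression.
- Section 3.1, survival contact continues for "survival status until death, lost to follow-up, withdrawal of consent to survival follow-up or the end of study".
- Section 8.1 limits the loss. Of a patient who withdraws consent to KN046 it says "the subject will be asked to continue tumor assessments if RECIST 1.1 defined confirmed PD does not occur". For withdrawal of consent more generally, "it must be clearly stated if the subject is also withdrawing their consent from the post-treatment follow-up assessments".
- Section 7.10: "Subjects will be followed for 2 years after removal from study or until death, whichever occurs first".

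No section says how a patient censored before the time point would enter a binomial numerator or denominator.

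**The concern.** A Clopper-Pearson interval is built from k successes among n patients whose outcomes are all known. A Kaplan-Meier rate with censoring before the time point is a product of conditional survival fractions and generally equals no such k/n. Following the explicit sentence means turning censored patients into counts. They can be called event-free, dropped from the denominator or called failures, and each choice gives a different rate and interval. The rate agrees with Kaplan-Meier only in special cases: nobody is censored, all censoring precedes the first event (dropped), or all censoring follows the last event before the time point (event-free).

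At stake is a reported 6- or 12-month rate and interval that do not belong to the curve printed beside them, with a convention that could be chosen after the data are seen.

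**Working it through.** **What is not affected.** The section gives no figure for this point. The Simon design in sections 12.1 and 12.2 reproduces and does not depend on it: early termination 0.95^10 = 0.599, expected sample size 10 + (1 - 0.5987) x 19 = 17.624, one-sided alpha 0.0468, power 0.8011.

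**Mechanism, hypothetical example (n = 29, 6 months).** There are 15 events (8 at 1.8, 4 at 3.7 and 3 at 5.5 months), 6 patients censored (at 1, 2, 2.5, 3, 4 and 4.5 months) and 8 followed event-free. The censoring is deliberately heavy (6/29) and is not a forecast.

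- Kaplan-Meier: 20/28 x 13/17 x 8/11 = 39.7%.
- Greenwood sum: 8/(28x20) + 4/(17x13) + 3/(11x8) = 0.0665. Half-width on the log(-log) scale: 1.96 x sqrt(0.0665)/|ln 0.397| = 0.547. The 95% CI is 20.3% to 58.6%.
- Clopper-Pearson, event-free: 14/29 = 48.3% (29.4% to 67.5%).
- Clopper-Pearson, dropped: 8/23 = 34.8% (16.4% to 57.3%).
- Clopper-Pearson, failure: 8/29 = 27.6% (12.7% to 47.2%).

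None of the three is an interval for 39.7%. With no censoring the estimates coincide: for 10/29, Clopper-Pearson gives 17.9% to 54.3% and log(-log) gives 18.2% to 51.4%.

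**How much loss is plausible.** The plan gives no dropout rate. Phase I disposition gives rough proxies.

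- Loss: 2/88 lost to follow-up (2.3%, Table 2-7) and 3/54 withdrew consent (5.6%, Table 2-1).
- Ceiling, all treatment stops other than progression or death: 5 + 2 + 9 = 16 of 88 (18.2%) and 1 + 7 + 3 + 5 + 1 = 17 of 54 (31.5%).

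**Operating characteristics.** Simulation with 40,000 trials per setting, n = 29, exponential event times and independent exponential censoring, calibrated to the expected share censored before the time point. The true 6-month PFS of 37.1% comes from the 4.2-month median quoted for pembrolizumab in section 2.1: exp(-6 ln2/4.2). Using it for this trial is an assumption.

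| 6-month PFS, true 37.1% | Event-free | Dropped | Failure |
|---|---|---|---|
| 5.6% censored: mean rate, % | 39.5 | 36.0 | 34.0 |
| 5.6% censored: coverage, % | 96.2 | 96.4 | 95.6 |
| 5.6% censored: rate >5 points from Kaplan-Meier, % of trials | 11 | 2 | 24 |
| 10% censored (assumed): mean rate, % | 41.4 | 34.9 | 31.4 |
| 10% censored (assumed): coverage, % | 94.7 | 96.5 | 92.6 |

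At 10% censored, Kaplan-Meier averages 37.2% with 94.9% coverage. The means can be checked by hand. If 31.4% are observed event-free to 6 months and 10% are censored, event-free gives 31.4 + 10 = 41.4 and dropped gives 31.4/0.90 = 34.9.

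- *12-month PFS, true 13.8%, 10% censored (assumed):* coverage is 87.0% / 96.6% / 96.2% for event-free / dropped / failure. Kaplan-Meier log(-log) covers 94.8% if undefined intervals count as misses. It is undefined in 3.3% of trials, where the curve reaches zero.
- *OS, 2.3% to 5.6% censored (6-month 88%; 12-month 65% and 50%, both assumed):* event-free or dropped is on average 0.1 to 1.7 points from Kaplan-Meier, with coverage of 95.7% to 98.0%. Under failure, 6-month OS of 88% with 5.6% censored is covered about 88% of the time.

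**Internal precedent.** The phase I rates in the efficacy results for KN046-CHN-001 (section 2.3.2.2) appear to use Kaplan-Meier log(-log) intervals. For 21.9% (4.6 to 47.3), the distances from estimate to limits are 17.3 and 25.4 points on the plain scale but 0.707 and 0.707 on the log(-log) scale. All nine PFS and OS rate intervals there are symmetric on that scale within 0.006. No k out of n up to 89 reproduces a printed rate with its interval under Clopper-Pearson (tolerance 0.15 points).

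**The case against.** The strongest reply is that this is loose wording. The sentence on 6- and 12-month rates follows the Kaplan-Meier sentence, and a statistician would probably report standard Kaplan-Meier output. That reading is reasonable and lowers the severity. It does not settle the matter, because it contradicts the one sentence that names an interval for these rates.

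Second, little loss may occur. Section 8.1 asks patients who withdraw from KN046 to continue scans, section 3.1 continues scans after treatment ends without progression, and section 7.10 plans two years of follow-up. This stands. At 2.3% to 5.6% loss, coverage for 6-month PFS is not harmed under any convention. Those proxies do not count new therapy started before progression, so they are not an upper bound for PFS.

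Third, the log(-log) interval is not uniformly better. For 6-month OS of 88% with no loss it covers 92.5%, counting as misses the 2.4% of trials where it is undefined, against 95.8% for Clopper-Pearson. If censoring is informative, Kaplan-Meier is biased too: with 10% censored just before progression and a true rate of 37.1%, it averages 42.8%. Both limits stand. They are a reason to state a fallback, not to keep a method that needs an unstated convention.

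A reader might infer that the planned intervals will fail badly. At 18.2% censored, 6-month PFS coverage under the failure convention falls to 82.6%, and at 31.5% to 51.4%. The documents do not support that as a forecast. Those shares count treatment stops up to data cut-off, not loss of follow-up before 6 months, and 8 of the 16 stops in KN046-CHN-001 were clinical deterioration.

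**Conclusion.** The point holds as a minor error of method in section 12.4.2. As written, the Clopper-Pearson sentence gives a rate and interval that generally do not match the Kaplan-Meier estimate once anyone is censored before the time point, and no other section resolves the conflict.

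At loss rates like those in phase I, the practical harm is mainly mismatch: for 6-month PFS the mean shifts by up to about 3 points (37.1 - 34.0 = 3.1, failure convention). Coverage suffers only in particular combinations, namely 6-month OS of 88% with 5.6% counted as failures (about 88%) and 12-month PFS with an assumed 10% counted as event-free (about 87%).

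These sizes rest on exponential event times, independent censoring, a borrowed median PFS and an unknown censoring rate; the 8-week scan schedule was not modelled.

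Two wider inferences are not supported. Clopper-Pearson is not wrong in itself: it suits ORR, and PFS or OS rates when every patient is observed. The primary conclusion is also not at risk, because ORR, the Simon design and the stopping rules do not use these intervals. How section 10.3 treats death in the PFS definition is a separate point.

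**What to change.** In section 12.4.2:

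1. Remove the clause that gives PFS and OS rates as examples from the Clopper-Pearson sentence. Keep the method for ORR and other fully observed proportions.
2. State that 6- and 12-month PFS and OS rates are Kaplan-Meier estimates with Greenwood-based 95% CIs on the log(-log) scale.
3. State a fallback for each case where that interval is undefined: no event before the time point, and a curve that reaches zero before it. For example, use an exact binomial interval when all patients are observed to the time point or to an event. Otherwise report the estimate and the number at risk, with the interval marked not estimable.

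The cost is a few sentences and standard software output, with no change to sample size or data collection. The small downside is coverage somewhat below 95% for high OS rates (about 92% to 93% at 88%, counting undefined intervals as misses). The change should be made before outcome data are reviewed.
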